## 2 STUDY OBJECTIVES AND ENDPOINTS

### 2.1 Objective and Endpoints

Table 2.1: Study Objectives and Endpoints

Objectives	Endpoints

Primary: To determine the safety and efficacy of GS-248 versus placebo on RP in subjects with SSc.
	
EFFICACY
 
Primary Efficacy: Mean change from baseline to week 4 in the number of Raynaud’s Phenomenon attacks per week.
 
Key secondary efficacy:
 
 
• Mean change from baseline to week 4 in the Raynaud’s Condition Score (RCS).
 
• Mean change from baseline to week 4 in the cumulative duration of Raynaud’s Phenomenon attacks.
 
• Mean change from baseline to week 4 in pain experienced during RP attacks.
 
 
Exploratory efficacy:
 
 
• Patient Global Impression of Change at week 4.
 
• Physician Global Impression of Change at week 4.
 
• Mean change in ASRAP Questionnaire score from baseline to week 4.
 
 
SAFETY
 
Safety Endpoints:
 
 
• Incidence of Adverse events.
 
• Incidence of Serious Adverse Events.
 
• Clinical laboratory and vital signs.
 

Secondary: To determine the efficacy of GS-248 on peripheral vascular blood flow in subjects with SSc and RP.
	
Secondary:
 
 
• Mean change from baseline to week 4 in peripheral blood flow prior to cold challenge and IMP administration.
 
• Mean change in peripheral blood flow from pre-IMP to post-IMP administration at Visit 2.
 

Objectives	Endpoints
	
 
• Mean change in recovery of peripheral blood flow after cold challenge from pre-IMP to post-IMP administration at Visit 2.
 
• Mean change from baseline to week 4 in recovery of peripheral blood flow after cold challenge.
 


Exploratory:
 
 
• To explore the PK of GS-248.
 
• To explore the efficacy of GS-248 on PGE2 formation in whole blood ex vivo.
 
• To explore the efficacy of GS-248 on formation of arachidonic acid metabolites.
 
• To explore the efficacy of GS-248 on inflammation and endothelial dysfunction.
 
• To explore the efficacy of GS-248 on platelet activation.
 
• To explore the efficacy of GS-248 on microvascular volume.
 
• To collect blood and urine for potential future analysis of inflammatory biomarkers and endothelial dysfunction (results will be reported at a later date).
 
	
Exploratory:
 
 
• GS-248 levels in plasma.
 
• Change in PGE2 level in whole blood ex vivo from baseline to week 4.
 
• Change in levels of PGEM, PGIM and TXM in urine from baseline to week 4.
 
• Change in levels of biomarkers in blood/plasma from baseline to week 4.
 
• Expression of platelet surface markers.
 
• Change in microvascular volume from baseline to week 4.
 

### 3 OVERALL DESIGN AND PLAN OF THE STUDY

[figure not shown]
#### 3.1 Overview

This is a randomised, double-blind, placebo-controlled study conducted in multiple sites in 4 countries in Europe. Approximately 80 subjects will be randomised in a 1:1 allocation to receive either GS-248 (120 mg) or placebo once daily, stratified to any of the 3 strata of background vasodilatory treatment (Ca-blockers, PDE-5 inhibitors, or no background vasodilatory treatment), with approximately 40 subjects in each treatment group.

The study will comprise a run-in/enrolment period, a treatment period, and a follow-up period, with a total of 5 study visits (see Overall Schedule of Assessments, [APPENDIX 2](#)).

Study assessments of thermography and pharmacodynamics will be conducted at pre-selected sites based on availability of technology (see Overall Schedule of Assessments, [APPENDIX 2](#)).

**Figure 1: Study Design**

*qd: once daily*

#### Run-in/Enrolment Period

Informed consent will be confirmed at Visit 1 (Screening Visit) from each subject and eligibility for the study will be established. Eligibility screenings will be conducted, including demographic data, subject medical history, a physical examination, and other procedures. In addition, blood and urine samples will be collected. Subjects will be issued with an eDiary to record information on a daily basis, including the number of Raynaud attacks and RCS (see Overall Schedule of Assessments, [APPENDIX 2](#)).

#### Treatment Period

On Day 1 (Visit 2, Baseline Visit) subjects will be reviewed for eligibility and subsequently randomised and receive their first dose of IMP under medical supervision at the study site. Study assessments, including PK sampling and safety, will be performed throughout this visit. In total, this visit will last for approximately 4 or 6 hours depending on whether the subject is enrolled in the cold challenge assessment or not. Subjects will be permitted to leave the study clinic for short time

periods between assessments as feasible but will be asked to remain on site. At the end of the visit, subjects will be dispensed sufficient amount of medication to last until the next study visit, scheduled for 14 ( $\pm 2$ ) days later.

Subjects will continue to fill in their eDiary throughout the Treatment Period.

On Day 15 ( $\pm 2$  days) subjects will return to the study site for Visit 3. Safety assessments, PK sampling and safety monitoring will be performed (see Overall Schedule of Assessments, [APPENDIX 2](#)). Treatment compliance will be checked, used bottle of IMP collected, and sufficient IMP for the remainder of the Treatment Period will be distributed. The visit will last approximately 1,5 hours.

Visit 4, End of Treatment Visit, will occur on Day 28 ( $-2/+1$  days), which will be the day subjects take their final dose of IMP, to be administered at the study site.

This visit will last for up to 5 hours, and for subjects undergoing rich PK sampling, this visit will last for up to approximately 9 hours. Additional safety and monitoring assessments will be performed (see [Appendix 4](#)).

The eDiary will be checked, and all IMP will be collected.

An ASRAP questionnaire will be completed by subjects, along with a Global Impression of Change, which is also completed by physicians.

### **Follow-Up Period**

The follow-up visit (Visit 5, Day 42-49) should occur 2-3 weeks after the last dose of IMP. Safety assessments will be performed (see Overall Schedule of Assessments, [APPENDIX 2](#)). Subjects will complete the final entry in their eDiary, and these will be collected. The visit will last approximately 1,5 hours.

## **3.2 Discussion of Study Design**

This is a randomised, double-blind, placebo-controlled, multi-center study. The aim of this study is to collect safety and efficacy data of GS-248 at a dose of 120 mg. To meet the objectives, a control group treated with placebo in a parallel group design will be applied. Power calculations have been performed to ensure the number of subjects needed is limited to a reasonable number. To maintain the integrity of the study data, a double-blind design has been selected. The safety and tolerability of GS-248 has already been studied in two Phase I studies that included healthy male and female subjects (age range 18-75 years) dosed up to 300 mg single dose and up to 180 mg for 10 days. In the present study, subjects with SSc and RP will be included to explore the possible treatment efficacy on RP and potential safety concerns of the IMP in a relevant population. The duration of the treatment period is considered long enough to be able to evaluate a significant effect on the primary endpoints based on previous experience in this patient population.

## **3.3 Dose justification**

The dose in the present study (120 mg once daily) is chosen to achieve a PK profile that completely blocks mPGES-1 generated PGE2 production and results in an increased PGI2 production, to secure a reliable read-out of the clinical efficacy of GS-248 in the selected study population.

GS-248 administered orally as single doses (40 mg to 300 mg) resulted in complete mPGES-1-mediated inhibition of PGE2 synthesis. Furthermore, GS-248 administered orally as multiple doses (60 mg and 180 mg) for 10 days resulted in an increase in the

vasodilatory and platelet-inhibitory prostacyclin, PGI2, as measured by the increased urinary excretion of the prostacyclin metabolite PGIM. The data also suggest a dose-dependent effect on the PGIM excretion from 20 mg to 180 mg.

The selected dosing regimen of repeated once daily doses of 120 mg GS-248 with the chosen lipid-based formulation in capsules is predicted to yield a systemic exposure lower than, or close to, that observed following 10 days of repeated dosing with an oral solution formulation at 180 mg/day.

In previous Phase I studies it was demonstrated that GS-248 was safe and well tolerated at single doses of 300 mg and at multiple doses of 180 mg daily for 10 days see current version of the [Investigator's Brochure](#).

### **3.4 End of Study Definition**

A subject is considered to have completed the study if he/she has completed all phases of the study including the Follow-up visit.

The end of the study is defined as the date of the last visit of the last subject in the study.

## 4 STUDY POPULATION

### 4.1 Inclusion Criteria

Individuals who meet all of the following criteria are eligible to participate in the study.

1. Subjects must provide signed and dated written informed consent before the conduct of any study-specific procedures.
2. Male and female subjects aged 18-75 years inclusive.
3. Systemic Sclerosis diagnosed according to European League Against Rheumatism (EULAR)/American College of Rheumatology (ACR) criteria ([van den Hoogen F et al. 2013](#)).  
*Subjects with signs of other autoimmune diseases (e.g. Sjögren's syndrome, myositis, rheumatoid arthritis) could be included if SSc is the dominating phenotype.*
4. Raynaud attacks typically  $\geq 7$  times per week during the last 4 weeks prior to screening despite background medication (only allowed vasodilatory therapy is calcium channel blockers or PDE-5 inhibitors).
5. Women of childbearing potential (WOCBP) must be using a highly effective method of contraception to avoid pregnancy throughout the study and for 4 weeks after the last dose of IMP in such manner that the risk of pregnancy is minimised (see [APPENDIX 12](#)).
6. Women must not be pregnant or breastfeeding.
7. Male subjects to agree to use condom in combination with use of contraceptive methods with a failure rate of  $< 1\%$  to prevent pregnancy and drug exposure of a partner, and refrain from donating sperm from the first date of dosing until 3 months after last dosing of the IMP.
8. Ability of subjects to participate fully in all aspects of this clinical trial.

In addition to fulfilling all eligibility criteria, subjects must fulfil the following criteria to be randomised:

- $\geq 7$  RP attacks during the last week of the run-in period as captured in the eDiary, with no more than 2 days without RP attacks.
- Compliance with the eDiary during the 7 most recent days prior to baseline (Visit 2), excluding the visit day itself, defined as having submitted  $\geq 5$  days of eDiary records (out of a possible 7 days) for RCS and RP during that period.

### 4.2 Exclusion Criteria

Individuals who meet any of the following criteria are not eligible to participate in the study.

1. SSc disease duration of greater than 120 months from first non-Raynaud manifestation
2. Current smokers or stopped smoking or used nicotine in any form  $< 3$  months prior to Visit 1.
3. Dose-change or initiation of vasodilating substances (calcium blockers or PDE-5 inhibitors) within 4 weeks prior to Visit 1. Subjects are not allowed to use a combination of calcium blockers and PDE-5 inhibitors from 4 weeks prior to Visit 1 and throughout the study.

4. Use of iloprost or other intravenous (iv) or po prostacyclin receptor agonist within 4 weeks prior to Visit 1.
5. Ongoing treatment with immunosuppressive therapies (other than mycophenolate) including, but not restricted to; cyclophosphamide, azathioprine, methotrexate, or cyclosporine, or use of those medications within 4 weeks of trial entry.  
*Note: Subjects could be included if they have been treated with a stable dose of mycophenolic acid during 4 weeks prior to Visit 1.*
6. Use of systemic corticosteroids during 4 weeks prior to Visit 1 and during the course of the study.
7. Use of moderate or strong CYP3A4 inhibitors within 5 terminal half-lives or one week, whichever is longer, prior to Visit 2. Examples of a moderate or strong CYP3A4 inhibitors are diltiazem, verapamil and grapefruit juice. See [Appendix 13](#) for more examples.
8. Concurrent serious medical condition, with special attention to cardiovascular conditions, which in the opinion of the Investigator makes the subject not suitable for this study.
9. Prolonged QTcF interval defined as a mean QTcF >450 msec at Visit 1, or at Visit 2 (prior randomisation).
10. Creatinine clearance <50 mL/min (determined by Cockcroft-Gault equation) at Screening (Visit 1).
11. Active digital ulcer (DU) within 4 weeks prior to Visit 1.
12. Have known allergies to any components of the GS-248 formulation.
13. Clinically meaningful laboratory abnormalities at Screening (Visit 1), as determined and documented by the Investigator.
14. Positive test results for HbsAg, HCVAb or HIV-1 and/or -2 antibodies at Screening (Visit 1)
15. Subjects known or suspected of not being able to comply with this trial protocol (e.g. due to alcoholism, drug dependency or psychological disorder).
16. Subject is mentally or legally incapacitated at the time of screening or has a history of clinically significant psychiatric disorders that would impact the subject's ability to participate in the study according to the Investigator.
17. Malignancy within the past 5 years except for in situ removal of basal cell carcinoma and cervical intraepithelial neoplasia grade I.
18. Planned major surgery within the duration of the study.
19. Blood donation (or corresponding blood loss) within 12 weeks prior to Visit 1.
20. Participation in another interventional clinical study within 4 weeks or given an experimental drug within 5 half-lives, whichever longest, prior to Visit 1.

Exclusion criterion for cold challenge:

- At Visit 2: Finger temperature below 27°C after acclimatising at an ambient temperature of 23°C ( $\pm 2^\circ\text{C}$ ) for a period of 20 minutes.

### 4.3 Screening Failures

Screening failures are defined as participants who consent to participate in the clinical study but are not subsequently entered in the study. A minimal set of screening failure information is required to ensure transparent reporting of screening failure participants to meet the Consolidated Standards of Reporting Trials (CONSORT) publishing requirements and to respond to queries from regulatory authorities.

Minimal information includes demography, screening failure details, eligibility criteria, and any serious adverse event (SAE).

If due to COVID-19 restrictions, Visit 2 cannot be conducted within 2 to 3 weeks of the Screening Visit re-screening is permitted. SSc Related Autoantibody tests do not need to be repeated: the initial Screening Visit result will be used. Re-screened subjects will be given a new subject number.

#### **4.4 Subject Identification and Randomization**

Each participating investigative study site will be assigned a 3-digit investigative study site number: the first digit will denote the country and the second and third digits will denote the site (e.g., 101, 102, 103, and up). Each subject will receive a 3-digit Screening number in sequential order at the Screening Visit after the consent form is signed (e.g., 001, 002, 003), regardless of the investigative study site at which the subject is enrolled. Each subject will then have a unique 6-digit study number comprising of the 3-digit Investigative study site number and 3-digit Screening number (e.g., 101-001, 101-002, 101-003), Enrolled subjects who fail Screening or discontinue study participation early, regardless of whether treatment was received or not, will retain their subject number and a new number will be assigned to the next enrolled subject.

Subjects will be randomised in a 1:1 allocation and stratified into 3 strata for use of background vasodilatory treatment Ca-blockers, background vasodilatory treatment PDE-5 inhibitors, or no background vasodilatory treatment, to receive either GS-248 (120 mg) or placebo.

Randomization will be performed by central randomization using the electronic Case Report Form (eCRF).

#### **4.5 Subject Withdrawal and Replacement**

As a result of treatment discontinuation, all subjects must complete an Early Termination visit (Visit 5) within 2-3 weeks after their last IMP dose.

There will be no replacement of withdrawn subjects.

The study participation of an individual subject must be discontinued, and no additional IMP doses given if the mean QTcF interval is above 480 msec post IMP administration at Visit 2, or above 500 msec at Visit 3.

The study participation of an individual subject may be discontinued prematurely for reasons such as:

- Adverse Event: Clinical or laboratory events that in the judgment of the investigator or the Sponsor and in the best interest of the subject constitute grounds for discontinuation. This includes serious and non-serious AE regardless of relation to IMP.
- Withdrawal of written informed consent: If a subject withdraws consent for disclosure of future information at the discontinuation of the study or after completion of the study, no further evaluations should be performed, and no additional data should be collected. The Sponsor may retain and continue to use data collected before the subject withdrew his/her consent. The reason for withdrawal of consent is only applicable if the subject denies any further contact with the site and no further data collection.

- Required treatment with any prohibited medication known or suspected to interfere with the pharmacological effect of IMP (see [Section 5.7](#)) as assessed by the Medical Monitor.
- Lack of study compliance: The subject's findings, or conduct, fails to meet protocol entry criteria or fails to adhere to the protocol requirements.
- Treatment unblinding.
- Any other condition which in the opinion of the Investigator no longer permits safe participation in the study.

A subject may discontinue participation in the clinical study at his/her own request at any time without stating a reason.

The Investigator can stop a subject's participation in the study at any time if continuation could lead to disadvantages for the subject which cannot be justified by the Investigator.

The reason for withdrawal of the subject must be documented by the Investigator together with all data collected until the day of premature study discontinuation including laboratory results and assessment of AEs.

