In the GS-1002 study a modest increase in mean QTcF (12.0 – 16.1 msec) was observed at time of peak concentrations, but there were no clinically significant patterns in ECG and no individual ECG was assessed as clinically significant abnormal. The QTcF findings are uncertain due to several factors including high variability, ECGs were collected only as single measurements, and no placebo groups were included. In the GS-1001 study there were no drug-related changes in QTcF. In addition, GS-248 did not demonstrate any cardiac repolarization risk in non-clinical studies including *in vitro* assay and *in vivo* studies in dogs (cardiovascular and 28 days toxicology studies) at plasma exposures exceeding those in the clinical studies. For further details please see current Investigator's Brochure.

A third study in healthy volunteers (GS-1003) was conducted during October and November 2021. This was a drug-drug-interaction study where 90 mg GS-248 was administered concomitantly with and without erythromycin, a moderate CYP3A4 inhibitor, at an oral dose of 500 mg three times daily. The pharmacokinetic results for GS-248 showed that the concurrent use of erythromycin caused an about eight-fold increase of the area under the plasma concentration curve and little less than three-fold increase of peak plasma concentrations. There is a sizable margin between the systemic exposures in the GS-1003 study and the maximum exposure limits established in toxicity studies at the so called No Observed Adverse Effect Level (NOAEL).

The current study concerns 28 (-2/+1) consecutive days of once-daily dosing with placebo or GS-248 (120 mg taken as 3 x 40 mg capsules in a lipid-based formulation), is predicted to yield a systemic exposure lower than, or close to, that observed following 10 days of repeated dosing with an oral solution formulation at 180 mg/day in the GS-1001 study. To secure the safety of the subjects in the study the following measures have been implemented:

- Subjects will receive their initial dose of study treatment in the study site, under medical supervision and they will be closely monitored.

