## **6.3 Other Exploratory Endpoints**

### **6.3.1 Pharmacokinetics**

Sparse PK sampling for determination of GS-248 levels in plasma will be performed on all subjects at Visit 2, Visit 3 and Visit 4.

One PK blood sample will be drawn at Visit 2 shortly after the ECG assessment is conducted post IMP administration and one PK blood sample will be drawn at Visit 3 any time during the visit.

At Visit 4 the IMP dose is administered at the study site. Two PK blood samples will be drawn from subjects in the sparse PK group. One sample is drawn immediately before IMP administration and the second sample is drawn either at 120 minutes after IMP administration or, if the subject is enrolled to cold challenge assessments, at 175 minutes after IMP administration.

In approximately 30 subjects, rich PK sampling will be performed at Visit 4, with an additional 6-7 PK samples to be drawn (see [APPENDIX 4](#)). Time points for all rich PK sampling at Visit 4 will be pre-dose, 30-, 60-, 90-, 120-, 175-, 240- and 360-min post dose. If feasible, one additional sample should also be drawn at 480 min or as late as possible post dose.

Exact times of IMP administration and time for sampling will be captured in the eDiary and eCRF.

Blood samples will be centrifuged, and separated plasma will be shipped to a bioanalytical laboratory.

The combined data from sparse and rich PK sampling will be incorporated into model-based population PK analyses, the results of which are to be reported separately.

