**APPENDIX 2: OVERALL SCHEDULE OF ASSESSMENTS**

	Visit 1 Screening Visit	Visit 2 Baseline Visit	Visit 3	Visit 4 EoT Visit	Visit 5 Follow-up or Early Termination Visit*
Activity	Enrolment	Treatment start	Treatment	End of Treatment	Follow-up
Day	-21 to -14	1	15 (±2 days)	28 (-2/+1 days)	42-49
Confirmation of Signed Informed consent	X				
Demographics	X				
Medical and surgical history	X				
Concomitant medication	X	X	X	X	X
Physical examination	X	X a	X a	X a	X
Nailfold capillaroscopy	X b				
Vital signs (BP, heart rate)	X	X	X	X	X
Weight/height	X				X c
ECG	X	X d	X		X
Clin chem and haematology	X	X	X	X	X
Thyroid hormones (free T3/T4, tot T4, TSH)	X				
Urinalysis – dipstick	X	X	X	X	X
SSc-related autoantibodies e	X				
Pregnancy test (WOCBP) f	X	X		X	X p
Inclusion/exclusion criteria	X	X			
Hepatitis B, C, HIV-test	X				
Drug screen g	X	X		X	
eDiary	X h				X i
ASRAP questionnaire (PRO)		X	X	X	X
Global Impression of Change (Subject/Physician)				X	
Adverse events	X	X	X	X	X
Randomisation		X			
IMP administration at site j		X		X	
IMP dispense to subjects		X	X		

	Visit 1 Screening Visit	Visit 2 Baseline Visit	Visit 3	Visit 4 EoT Visit	Visit 5 Follow-up or Early Termination Visit*
Activity	Enrolment	Treatment start	Treatment	End of Treatment	Follow-up
Day	-21 to -14	1	15 (±2 days)	28 (-2/+1 days)	42-49
IMP collection and compliance			X	X	
PK sampling (sparse)		X	X	X	
AA metabolites, and urine creatinine k		X		X	
Blood biomarker sampling l		X		X	
Biobank samples – urine and blood		X		X	
Assessments below will be conducted at pre-selected sites					
Finger temperature		X			
Cold challenge, thermography		X m		X	
PK sampling (rich)				X	
PGE 2 levels in whole blood		X		X	
Platelet activation (FACS) n		X		X	
Microvascular volume (D-OCT)		X o	X	X o	X

\* Also, the Early Termination visit, if applicable.

- Abbreviated examination (minimally to include statement regarding DUs).
- Could be performed at Visit 2 if not feasible at Visit 1.
- Only weight (not height) to be recorded at this visit.
- Two ECG assessments will be performed, one pre- and another 170 min post-IMP administration.
- Analysis of antinuclear antibodies (ANA), Scl-70 antibody (anti-topoisomerase I) and anti-centromere antibodies (ACA)

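### The only ECG under repeated dosing (Visit 3, on which the 500 msec rule rests) has no set time after dose, although the QTcF rise behind the rule was seen at peak concentration

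*Protocol*

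**What the plan says.** Protocol section 1.3 gives the background: "In the GS-1002 study a modest increase in mean QTcF (12.0 – 16.1 msec) was observed at time of peak concentrations". It qualifies this at once: "The QTcF findings are uncertain due to several factors including high variability, ECGs were collected only as single measurements, and no placebo groups were included". It adds: "In the GS-1001 study there were no drug-related changes in QTcF". Non-clinical work is also reported as showing no repolarisation risk. Section 1.3 then lists QTcF withdrawal limits among the measures that protect subjects, and section 4.5 makes them mandatory: a mean QTcF "above 480 msec post IMP administration at Visit 2, or above 500 msec at Visit 3".

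The ECGs to which these limits apply are scheduled as follows.

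- **Visit 2.** Appendix 2: "Two ECG assessments will be performed, one pre- and another 170 min post-IMP administration". Appendix 3 and SAP 8.4 agree.
- **Visit 3.** Section 7.1.3 and Appendix 2 list an ECG with no time relative to dose. SAP 8.4 gives only the visit and day. Section 6.2.7 refers back to Appendix 2. The detailed time schedules (Appendices 3 and 4) cover Visits 2 and 4 only. Under section 5.2 that day's dose is self-administered. For PK, section 6.3.1 says "one PK blood sample will be drawn at Visit 3 any time during the visit".
- **Visit 4.** The dose is given on site with timed post-dose PK samples, but no ECG appears in section 7.1.4, Appendix 2, Appendix 4 or SAP 8.4.
- **Visit 5.** An ECG is taken 2 to 3 weeks after the last dose.

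**The concern.** If the drug prolongs QTcF mainly around peak concentration, an ECG is informative only when its distance from the dose is known and preferably fixed. The plan does this for the first dose and then drops it for repeated dosing. The two limits in section 4.5 are therefore applied to readings taken under different conditions: one close to expected peak, the other at whatever interval the appointment happens to give.

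Two things are at stake. First, the only scheduled QTcF withdrawal check after Day 1 could miss a peak effect. Second, safety is part of the primary objective. The SAP 8.4.2 categories for absolute QTcF and change from baseline rest, for on-treatment data after Day 1, on the Visit 3 reading alone. An unremarkable table could reflect no effect or an off-peak reading, and the planned outputs could not tell these apart. The trial has triplicate ECGs and a placebo arm, two of the features whose absence made the GS-1002 finding uncertain, so it is otherwise well placed to clarify it.

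**Working it through.** The plan states no figure to reproduce here. The check sets the schedules side by side and does simple day and minute arithmetic.

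**1. Expected peak.** Protocol section 6.3.2 places a post-dose D-OCT scan at expected Cmax. The Appendix 2 footnotes time it at 175 min. The Visit 2 post-dose ECG is at 170 min, and 175 − 170 = 5 min. The 480 msec limit is thus read close to expected peak, after a first dose.

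**2. ECG count.** Protocol Appendix 2 and SAP 8.4 agree.

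| ECG | Dosing state | Time after dose |
|---|---|---|
| Visit 1 | before treatment | not applicable |
| Visit 2, pre-dose | before treatment | not applicable |
| Visit 2, post-dose | first dose | 170 min |
| Visit 3 | repeated dosing | not set |
| Visit 4 | repeated dosing | no ECG |
| Visit 5 | 2 to 3 weeks off drug | not applicable |

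ECGs under repeated dosing: 1. Of these, timed to peak: 0.

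**3. Dosing days after the last on-treatment ECG.** Visit 3 is Day 15 ± 2 (Days 13 to 17). The last dose is at Visit 4, Day 28 −2/+1 (Days 26 to 29).

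- Shortest: 26 − 17 = 9 days
- Nominal: 28 − 15 = 13 days
- Longest: 29 − 13 = 16 days

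**4. Can Visit 3 reach 170 min as now run?** The visit lasts about 1.5 hours, or 90 min (section 3.1). A dose taken on arrival allows an ECG no later than about 90 min after dose. An ECG at 170 min inside the visit needs a home dose between 170 − 90 = 80 min and 170 min before arrival. That is feasible with morning dosing, but nothing in the plan arranges it.

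**5. Filters before Visit 3.** Section 4.2 excludes a mean QTcF above 450 msec at Visit 1 or pre-dose at Visit 2. A subject at that ceiling with the GS-1002 mean rise would be expected at 450 + 12.0 = 462.0 to 450 + 16.1 = 466.1 msec, below both limits. Subjects who continue must also have been at or below 480 msec at the Day 1 post-dose ECG.

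**The case against.** The strongest case against has four parts.

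- **The signal is weak.** The sponsor calls GS-1002 uncertain. GS-1001 included 10 days at up to 180 mg/day and showed no drug-related change, and exposure here is predicted to be lower than or close to that regimen. This stands, and it limits how serious the point is. It does not supply a peak-timed reading under repeated dosing in this population and capsule formulation.
- **The limits are not contradictory.** Sections 1.3 and 4.5 agree with each other, and the protocol and SAP agree on the schedule. This also stands. The gap lies between the rationale and the schedule.
- **Some Visit 3 ECGs will fall near peak.** Dosing is in the morning, and no text asks subjects to hold the Day 15 dose. A reader might infer that peak QTcF under repeated dosing will never be seen, or that Visit 3 is a trough reading. The documents support only that the interval is uncontrolled.
- **Entry and Day 1 limits already screen subjects.** A reader might subtract the GS-1002 rise from 500 (500 − 16.1 = 483.9; 500 − 12.0 = 488.0) and conclude that Visit 3 readings from about 484 to 488 msec upward hide peaks above 500. The documents do not support such a band. With the drug effect absent, the reading is the subject's undrugged QTcF, which had to be at or below 450 msec at entry. Reaching 483.9 off peak needs 483.9 − 450 = 33.9 msec or more from variability or another cause, for which no figure is given.

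A reader might also take the Visit 4 text in section 3.1, "Additional safety and monitoring assessments will be performed", as an unkept promise of an ECG. It names none, and Visit 4 does include vital signs, laboratory tests, an abbreviated physical examination and adverse event collection.

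The COVID-19 provisions in section 7.1.6 do not fill the gap. Their on-site ECG applies when a visit cannot be held as scheduled. For Visits 3 and 4 it follows the stop of study medication, and it is not timed to dose.

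**Conclusion.** The concern holds as a gap in timing and reporting. None of the ECGs under repeated dosing (0 of 1) is timed to the concentration peak that section 1.3 gives as the setting of the QTcF rise, and the last 9 to 16 days of dosing have no scheduled ECG. QTcF at peak under repeated dosing will be observed only by chance. The SAP 8.4 on-treatment categories after Day 1 rest on one reading at an unknown interval from dose.

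The untimed reading applies to all of the approximately 40 subjects on active treatment, but that is not the number who could pass the 500 msec check wrongly. That number is reduced by the 450 and 480 msec filters. It cannot be estimated from the documents, which give neither the within-subject variability of QTcF nor its behaviour under repeated dosing.

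The conclusion rests on two assumptions: that 175 min is a fair marker of Cmax, as the protocol itself treats it, and that any QTcF effect follows concentration, as the GS-1002 description suggests but does not establish. It is an inexpensive improvement that should be made. It does not show that the limits are wrong.

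**What to change.** 1. Reconcile the peak-concentration rationale in protocol section 1.3 with the Visit 3 and Visit 4 ECG schedule. One way is to book the existing Visit 3 triplicate ECG relative to that day's dose, at the post-dose time the protocol already uses at Visit 2.
2. Record the clock time of the Visit 3 ECG in the eCRF and derive time since dose. The eDiary already captures dose time (sections 5.6 and 8.4). Appendices 3 and 4 require exact times in the eCRF for Visits 2 and 4; Visit 3 has no such schedule.
3. In SAP 8.4, present QTcF values, changes and categories by time since dose.

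Leave the Visit 3 PK sample free within the visit. Its spread of times serves the population PK analysis (section 6.3.1), and tying it to the ECG would lose that. No Visit 4 procedure is proposed. An ECG attached to the existing PK sample there would fall at 120 min for subjects outside cold challenge, about 80 − 50 = 30 of 80 on the planned numbers. The msec limits, and whether each suits the timing of its ECG, are for the sponsor to decide.

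**Cost.** Amendment wording, one eCRF field if not already present, and a booking instruction; no added procedure or sample. Visit 3 appointments become less flexible. Because the visit lasts about 1.5 hours, the timing depends on a self-reported home dose.
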